#### Archiving of the clinical trial master file

Unless other law requires archiving for a longer period, the sponsor and the investigator shall archive the content of the clinical trial master file for at least 25 years after the end of the clinical trial.

[figure not shown]
### **10.15 Publications**

If based on preliminary data, or on completion of the study, the data warrant publication/presentation according to a judgement by the Global Coordinating Investigator after collaborative discussions with other involved Investigators (meaning such Investigators who have recruited patients to the trial or have had a significant participation in the trial by other means), the results may be published/presented, under the auspice of the Global Coordinating Investigator, in a recognized scientific journal, or at a scientific conference, subject to the provisions of the following process:

[figure not shown]
- no publication based on the results obtained at an individual trial site (or group of sites) shall be made before the first multicenter publication or presentation unless otherwise agreed in writing. Notwithstanding the foregoing, if a multicenter publication is not published within twelve (12) months after completion of the clinical trial and final lock of the clinical trial database at all research sites that are part of the multicenter clinical trial or any earlier termination or abandonment of the clinical trial, or if the Sponsor informs the Principal Investigator that such multicenter publication will not take place, or if publication has been agreed otherwise, the Principal Investigator shall have the right to publish or present the methods and results of the clinical trial,

[figure not shown]

[figure not shown]
- in case a publication/presentation is proposed the Global Coordinating Investigator shall discuss the proposed publication/presentation with the Sponsor, and give the Sponsor a relevant time (depending on the planned publication situation; e.g. referred journal, or scientific conference abstract, submission) to support with data collection and analyses which could be the basis for a publication,
- the Sponsor should have adequate time for review of proposed abstracts, manuscripts, and/or other presentation materials before submissions (time is dependent on the planned publication situation; adequate time for review before submission of a complete manuscripts to a referred journals can be considered as 30 days, to respond with any requested revisions, including the deletion of confidential information which must be done).

[figure not shown]

[figure not shown]

## 12 APPENDICES

### 12.1 Appendix 1: Criteria for measurement of tumor response and progression; RECIST and iRECIST

Response and progression in this trial will be evaluated using the revised international criteria (1.1) proposed by the Response Evaluation Criteria in Solid Tumors (RECIST) committee [36] as well as the modified iRECIST guidelines [37]. Investigators should especially note the different requirements for confirmatory scans as well as follow-up for the two criteria.

#### RECIST 1.1 Response and Evaluation Endpoints

##### Measurable Disease

Measurable tumor lesions (nodal, subcutaneous, lung parenchyma, solid organ metastases) are defined as those that can be accurately measured in at least one dimension (longest diameter to be recorded) as  $\geq 20$  mm with chest x-ray and as  $\geq 10$  mm with CT scan or clinical examination. Bone lesions are considered measurable only if assessed by CT scan and have an identifiable soft tissue component that meets these requirements (soft tissue component  $\geq 10$  mm by CT scan). Malignant lymph nodes must be  $\geq 15$  mm in the short axis to be considered measurable; only the short axis will be measured and followed. All tumor measurements must be recorded in millimeters (or decimal fractions of centimeters). Previously irradiated lesions are not considered measurable unless progression has been documented in the lesion.

##### Non-measurable Disease

All other lesions (or sites of disease), including small lesions are considered non-measurable disease. Bone lesions without a measurable soft tissue component, leptomeningeal disease, ascites, pleural/pericardial effusions, lymphangitis cutis/pulmonis, inflammatory breast disease, lymphangitic involvement of lung or skin and abdominal masses followed by clinical examination are all non-measurable. Lesions in previously irradiated areas are non-measurable, unless progression has been demonstrated.

##### Target Lesions

When more than one measurable tumor lesion is present at baseline all lesions up to a maximum of 5 lesions total (and a maximum of 2 lesions per organ) representative of all involved organs should be identified as target lesions and will be recorded and measured at baseline. Target lesions should be selected on the basis of their size (lesions with the longest diameter), be representative of all involved organs, but in addition should be those that lend themselves to reproducible repeated measurements. Note that pathological nodes must meet the criterion of a short axis of  $\geq 15$  mm by CT scan and only the short axis of these nodes will contribute to the baseline sum. All other pathological nodes (those with short axis  $\geq 10$  mm but  $< 15$  mm) should be considered non-target lesions. Nodes that have a short axis  $< 10$  mm are considered non-pathological and should not be recorded or followed. At baseline, the sum of the target lesions (longest diameter of tumor lesions plus short axis of lymph nodes: overall maximum of 5) is to be recorded.

After baseline, a value should be provided on the CRF for all identified target lesions for each assessment, even if very small. If extremely small and faint lesions cannot be accurately measured but are deemed to be present, a default value of 5 mm may be used. If lesions are too small to measure and indeed are believed to be absent, a default value of 0 mm may be used.

*Non-target Lesions*

All non-measurable lesions (or sites of disease) plus any measurable lesions over and above those listed as target lesions are considered non-target lesions. Measurements are not required but these lesions should be noted at baseline and should be followed as “present” or “absent”.

*Response*

All patients will have their BEST RESPONSE from the start of study treatment until the end of treatment classified as outlined below:

*Complete Response (CR)*: disappearance of target and non-target lesions and normalization of tumor markers. Pathological lymph nodes must have short axis measures <10 mm (Note: continue to record the measurement even if <10 mm and considered CR). Residual lesions (other than nodes <10 mm) thought to be non-malignant should be further investigated (by cytology, specialized imaging, or other techniques as appropriate for individual cases) before CR can be accepted. Confirmation of response is only required in non-randomized studies.

*Partial Response (PR)*: at least a 30% decrease in the sum of measures (longest diameter for tumor lesions and short axis measure for nodes) of target lesions, taking as reference the baseline sum of diameters. Non target lesions must be non-PD. Confirmation of response is only required in non-randomized studies.

*Stable Disease (SD)*: Neither sufficient shrinkage to qualify for PR, nor sufficient increase to qualify for PD taking as reference the smallest sum of diameters on study.

*Progressive Disease (PD)*: at least a 20% increase in the sum of diameters of measured lesions taking as references the smallest sum of diameters recorded on study (including baseline) AND an absolute increase of  $\geq 5$  mm. Appearance of new lesions will also constitute progressive disease (including lesions in previously unassessed areas). In exceptional circumstances, unequivocal progression of non-target disease may be accepted as evidence of disease progression, where the overall tumor burden has increased sufficiently to merit discontinuation of treatment or where the tumor burden appears to have increased by at least 73% in volume. Modest increases in the size of one or more non-target lesions are NOT considered unequivocal progression. If the evidence of PD is equivocal (target or non-target), treatment may continue until the next assessment, but if confirmed, the earlier date must be used.

*Confirmatory measurement/duration of response*

*Confirmation*: In non-randomized trials where response is the primary endpoint, confirmation of PR and CR is required to ensure responses identified are not the result of measurement error. This will also permit appropriate interpretation of results in the context of historical data where response has traditionally required confirmation in such trials. However, in all other circumstances, i.e. in randomized trials (phase II or III) or studies where stable disease or progression are the primary endpoints, confirmation of response is not required since it will not add value to the interpretation of trial results. However, elimination of the requirement for response confirmation may increase the importance of central review to protect against bias, in particular in studies which are not blinded.

In the case of SD, measurements must have met the SD criteria at least once after study entry at a minimum interval (in general not less than 6–8 weeks) that is defined in the study protocol.

**Duration of overall response:** The duration of overall response is measured from the time measurement criteria are first met for CR/PR (whichever is first recorded) until the first date that recurrent or progressive disease is objectively documented (taking as reference for progressive disease the smallest measurements recorded on study). The duration of overall complete response is measured from the time measurement criteria are first met for CR until the first date that recurrent disease is objectively documented.

**Duration of stable disease:** Stable disease is measured from the start of the treatment (in randomized trials, from date of randomization) until the criteria for progression are met, taking as reference the smallest sum on study (if the baseline sum is the smallest, this is the reference for calculation of PD). The clinical relevance of the duration of stable disease varies in different studies and diseases. If the proportion of patients achieving stable disease for a minimum period of time is an endpoint of importance in a particular trial, the protocol should specify the minimal time interval required between two measurements for determination of stable disease. Note: The duration of response and stable disease as well as the progression-free survival are influenced by the frequency of follow-up after baseline evaluation. It is not in the scope of this guideline to define a standard follow-up frequency. The frequency should take into account many parameters including disease types and stages, treatment periodicity and standard practice. However, these limitations of the precision of the measured endpoint should be taken into account if comparisons between trials are to be made.

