**Table 7 : Integration of target, non-target and new lesions into response assessment**

Target Lesions	Non-Target Lesions	New Lesions	Overall Response	Best Response for this Category also Requires
Target lesions ± non target lesions				
CR	CR	No	CR	Normalization of tumour markers, tumour nodes <10 mm
CR	Non-CR/Non-PD	No	PR	
CR	Not all evaluated	No	PR	
PR	Non-PD/ not all evaluated	No	PR	
SD	Non-PD/ not all evaluated	No	SD	Documented at least once $\geq 4$ wks. from baseline
Not all evaluated	Non-PD	No	NE	
PD	Any	Any	PD	
Any	PD	Any	PD	
Any	Any	Yes	PD	
Non target lesions ONLY				
No Target	CR	No	CR	Normalization of tumour markers, tumour nodes <10 mm
No Target	Non-CR/non-PD	No	Non-CR/non-PD	
No Target	Not all evaluated	No	NE	
No Target	Unequivocal PD	Any	PD	
No Target	Any	Yes*	PD	
Note: Patients with a global deterioration of health status requiring discontinuation of treatment without objective evidence of disease progression at that time should be reported as "symptomatic deterioration". This is a reason for stopping therapy, but is NOT objective PD. Every effort should be made to document the objective progression even after discontinuation of treatment.				
*Investigators should record all new lesions; if the new lesion is felt to be equivocal, treatment may be continued pending further assessments – see table 2.				

[figure not shown]

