### 7.8.1 General aspects of response related endpoints

The response assessments during the treatment period follow the scheduled CTs post

baseline, planned for the visits at study weeks 9, 17, 25 (+/- 4 days), and from Week 25 onwards every 8 weeks (+/- 4 days). Unscheduled CT assessments as well as planned CT scans performed on the day of study drug administration [REDACTED]

[REDACTED] are also possible. For patients who are discontinuing all study treatment without having had confirmation of progressive disease (PD) according to iRECIST criteria [Seymour et al], CT assessments are scheduled every 8 weeks (+/- 4 days) after the latest performed CT assessment during the time period they received study treatment.

If not otherwise stated, all response assessments collected by investigator (local assessments) during the study will be considered, regardless of whether they come from scheduled or unscheduled assessments and if they were assessed during or after study treatment.

In principle, any further anti-cancer treatment during the study, i.e. prior to the individual study treatment termination, is prohibited. If nevertheless a patient is treated with further anti-cancer treatment during the study, the inclusion of CT assessments after introduction of further anti-cancer treatment in the derivation of response related and time to event endpoints will be agreed on and documented during the DRM. Also, the non-trial systemic anti-cancer treatments defined in Section 7.8.5 and 7.8.6 will be confirmed during the DRM.

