#### **7.8.5 Duration of response (DOR) & Duration of disease control (DDC)**

DOR can only be determined for patients with OR as defined above.

According to RECIST, the DOR is measured from the time at which the measurement criteria according to RECIST are first met for CR or PR (whichever is first recorded) until the first date that PD is objectively documented according to RECIST (see Section 7.8.6 for details).

- According to iRECIST, the DOR is measured from the time at which the measurement criteria according to iRECIST are first met for iCR or iPR (whichever is first recorded) until the first date progression criteria according to iRECIST are met (see Section 7.8.6 for details).

Patients alive with no progression will be censored following the same censoring rules as for PFS (see Section 7.8.6). DDC can only be determined in patients with disease control as defined above. DDC according to RECIST/iRECIST is measured from the start of study treatment until the first date that PD is objectively documented according to RECIST/iRECIST (see Section 7.8.6 for details); alternatively censoring is applied according to the rules for PFS.

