#### **7.8.6 Progression-free survival (PFS) and overall survival (OS)**

According to RECIST, PFS is defined as the period from the first dose of study drug until PD or death from any cause (whatever occurs first).

PFS is defined as the period from the first dose of study drug until the first time one of following events occurs

- Progression criteria according to iRECIST/RECIST met

- Start of non-trial systemic anti-cancer treatment (which is regarded as progression according to the protocol).
- death from any cause [REDACTED] after last post-baseline CT assessment [REDACTED] after first dose of study drug, if no post-baseline CT assessment is available.

Non-trial systemic anti-cancer treatment is defined as concomitant or post-study treatment/medication that is classified as chemotherapy in the eCRF. Mitotane therapy is not considered as non-trial system anti-cancer treatment.

According to RECIST the progression criteria is met at the first date of post-baseline CT assessment with PD documented as response, if not more than one scheduled CT assessment is missing or not evaluable before this CT assessment and the previous CT assessment was performed within [REDACTED] to this CT assessment.

According to iRECIST the progression criteria is met at the date of CT assessment with response documented as iUPD for that the next CT assessment documents iCPD as response (without any intervening assessments with other outcome), i.e. PD is confirmed, and if not more than one scheduled CT assessment is missing or not evaluable before the CT assessment with iUPD documented and the previous CT assessment was performed within [REDACTED] to CT assessment with IUPD documented. If progression is not confirmed and there is no subsequent CT assessment with iSD, iPR or iCR as response then the iUPD date will still be used as date of progression met in the following scenarios:

- no further response assessments are done or
- the next timepoint responses are all iUPD, and iCPD never occurs.

Non-trial systemic anti-cancer treatment is defined as concomitant or post-study treatment medication that is classified as chemotherapy in the eCRF. Mitotane therapy is not considered as non-trial system anti-cancer treatment.

Patients without an event as defined above will be censored based on the rules in Table 3.

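### The SAP's RECIST progression date omits the protocol's rule that confirmed equivocal progression takes the earlier date, so RECIST PFS can run up to about one scan interval too long in affected patients

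*Protocol*

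**What the plan says.** **Protocol.** Appendix 12.1, in its RECIST 1.1 definition of progressive disease, deals with target or non-target evidence of progression that is equivocal: "treatment may continue until the next assessment, but if confirmed, the earlier date must be used". The same paragraph accepts non-target progression only when it is unequivocal, and says that modest growth of non-target lesions does not qualify. A footnote to Table 7 covers new lesions separately: "if the new lesion is felt to be equivocal, treatment may be continued pending further assessments". Protocol 7.7 sends the reader to this appendix for the criteria, and Protocol 3.2.2 names PFS by RECIST 1.1 as a secondary endpoint.

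**SAP.** Section 7.8.6 reads: "According to RECIST the progression criteria is met at the first date of post-baseline CT assessment with PD documented as response". It adds conditions on missed scans and on the time since the previous CT, but nothing that moves the date to an earlier, equivocal scan. For the other criterion the same section does use the earlier scan: "According to iRECIST the progression criteria is met at the date of CT assessment with response documented as iUPD", provided the next CT documents confirmed progression.

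Duration of disease control (DDC) takes its end date from 7.8.6: "DDC according to RECIST/iRECIST is measured from the start of study treatment until the first date that PD is objectively documented". RECIST duration of response (DOR) points to the same section, and time-to-OR (SAP 7.8.4) censors non-responders at the PFS event date.

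**The concern.** The protocol's dating rule is mandatory, and the SAP's operative definition of RECIST progression does not carry it over. The SAP handles delayed confirmation for iRECIST, so its silence on RECIST looks like an omission. Programmed as written, the derivation takes the first scan coded PD. If the earlier equivocal scan was recorded as something else, the event falls one assessment later than the protocol requires.

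The date feeds the Kaplan-Meier curves, the medians, the 6- to 24-month estimates and any Cox model for RECIST PFS (SAP 7.8.7). One scheduled interval is about 1.8 months. That is not small in a disease where Protocol 1.2 quotes median PFS of 2.1 and 2.6 months for two checkpoint-inhibitor trials, and the cohorts are small enough for one patient to show. Assessment is local and open-label, and treatment may continue past RECIST progression, so equivocal scans are plausible.

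**Working it through.** **1. Scan calendar.** SAP 7.8.1 schedules CTs at weeks 9, 17 and 25 and then every 8 weeks, each with a window of 4 days either side. With day = (week − 1) × 7 + 1, weeks 9, 17, 25 and 33 fall on days 57, 113, 169 and 225. Day 169 for week 25 matches the day stated in Protocol 3.2.1. The gap is 225 − 169 = 56 days.

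**2. The two rules on one sequence** (equivocal at week 17, confirmed at week 25):

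| Code recorded at week 17 | Protocol date | SAP date | Difference |
|---|---|---|---|
| SD | day 113 | day 169 | 56 days |
| NE | day 113 | day 169 | 56 days |
| PD, or re-coded PD | day 113 | day 113 | 0 |

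The NE row assumes that the later PD still passes the SAP's rules on missing or non-evaluable scans and on the interval between CTs.

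**3. Which row applies.** For non-target disease the appendix requires unequivocal progression, so an equivocal change is non-PD. Table 7 then gives SD or PR overall when the target lesions are SD or PR and there is no new lesion. Table 7 has no equivocal category. No readable text calls for the earlier scan to be re-coded. SAP 6.1 makes no imputations by default. Read as written, this leads to the later date. A new lesion is different, because Table 7 already gives PD for it.

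**4. Range of the gap per affected patient** (30.5 days per month, the SAP's conversion elsewhere):
- Scheduled scans on time: 56 / 30.5 = 1.8 months.
- Scheduled scans at the window edges: 56 − 8 = 48 days to 56 + 8 = 64 days, or 1.6 to 2.1 months.
- Unscheduled confirming scan at 4 weeks: 28 / 30.5 = 0.9 months. SAP 7.8.1 counts unscheduled scans.
- Shorter still if non-trial systemic anti-cancer therapy starts before the confirming scan, since SAP 7.8.6 counts that start as a PFS event.

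**5. Effect on 6-month RECIST PFS.** Take 6 × 30.5 = 183 days. A patient equivocal at week 25 (day 169) and PD at week 33 (day 225) has an event before 183 days under the protocol rule and is event-free at 183 days under the SAP rule. Ignoring censoring, one such patient moves the estimate by:
- 1/26 = 3.8 percentage points in non-randomized Cohort 2A;
- 1/13 = 7.7 percentage points in Cohort 2A-I.

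Cohort sizes are from SAP 4.2.

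**6. Average over a cohort.** The share of affected patients is not given. For assumed shares of 0%, 10% and 30%, the mean shift is 0, 0.8 and 2.4 weeks at an 8-week gap (share × 8), or 0, 0.4 and 1.2 weeks at a 4-week gap (share × 4).

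**The case against.** The strongest reply is that neither document says how an equivocal scan is recorded. The appendix guides the investigator and the SAP analyses what the investigator enters. A site that follows the appendix could correct the earlier response to PD by query, and the SAP rule would then return the earlier date. That stands, and it makes the discrepancy conditional. It does not remove it, because nothing readable requires the correction and the non-target criteria point to a non-PD code.

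Other parts of the reply also stand:
- **Target lesions.** Progression there is numeric (at least 20% and 5 mm), which leaves less room for an equivocal reading. The protocol sentence still names target disease.
- **New lesions.** Table 7 already makes them PD, and the dating sentence covers only target and non-target findings.
- **DOR.** The protocol's own end point is "until the first date that recurrent or progressive disease is objectively documented", almost the SAP's wording, so the conflict is weaker there. DDC is not defined in the readable protocol; it inherits the SAP date.
- **Redaction.** SAP 5.3, on changes from planned analyses, and the time windows in 7.8.6 are blacked out, so a provision there cannot be excluded.

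A reader might infer that RECIST times are always too long. The documents do not support that. An equivocal scan coded NE counts towards the missing-scan rule, and a later PD may then be censored at an earlier CT. A reader might also infer that the combination is flattered against the published checkpoint-inhibitor results. The documents do not say how those trials dated equivocal progression, and the readable text plans no formal RECIST comparison with them.

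**Conclusion.** The point holds as a gap between the protocol's rule and the SAP's operative definition. A mandatory dating rule for RECIST progression is absent from SAP 7.8.6. Unless the earlier scan is coded or re-coded PD, RECIST PFS in an affected patient can run up to about one scan interval too long, with the range shown in the working. DDC and the time-to-OR censoring date follow through their references to 7.8.6, and DOR follows more weakly.

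The per-patient effects of 3.8 and 7.7 points are for one assumed patient with no censoring. They are not bounds, and the true number of such patients may be zero. It would be wrong to read a demonstrated 8-week bias into this, because the recorded coding is not visible. It would also be wrong to extend it to the phase 2 primary endpoint, which is iRECIST-based; for iRECIST the SAP already dates confirmed progression at the first, unconfirmed scan. The matter concerns named secondary endpoints and should be corrected because the correction is cheap.

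**What to change.** Add to SAP 7.8.6, after the RECIST progression rule:

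*When a RECIST PD confirms a target or non-target finding that was judged equivocal at the immediately preceding assessment, the progression date is the date of that preceding assessment.*

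Do not extend this to new lesions. State also how an equivocal RECIST assessment is to be coded, so that the rule and the data agree. DOR, DDC and time-to-OR censoring then follow through their existing references.

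No field for equivocal findings is shown in the readable text, and Appendix 12.1 follows non-target lesions only as present or absent. The cases may therefore need review rather than programming alone. Identify them with a query to the investigator where the eCRF is silent, and record the decisions at the data review meeting. That meeting already rules on some CT handling (SAP 7.8.1), and its minutes are signed before database lock (SAP 5.2).

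The cost is one or two sentences and a little case review. RECIST PFS may become slightly shorter. If sites already re-code the earlier scan, the added text confirms the practice and changes no result.
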